Initially, many surgeons used larger catheters (22Fr) to promote an open anastomosis, but some groups have found this to be associated with fossa navicularis strictures⁷. As a result, most surgeons now leave an 18 or 20 French Foley catheter to drainage for approximately 1 week post-operatively⁷. Interestingly, no study to our knowledge has assessed whether catheter size has an impact on continence, post-operative pain, and long term complication rates such as bladder neck contracture. We would expect urinary flow rates to differ based on urethral or catheter diameter according to Poiseuille's law, and several studies have shown this to be the case⁸.

In this study, we will randomize our RALP patients to either a 16 French or 20 French catheter to assess the effect of catheter size on post-operative catheter pain. Additionally, we will investigate pads per day, urinary flow rates, post-void residual urine volume (PVR), International Prostate Symptom Scores (IPSS) and Quality of Life (QoL) score, as well as long term complications. We hypothesize that patients with a smaller catheter will have improved pain scores and less opioid use. In terms of return to continence, we predict that use of a smaller urethral catheter will decrease flow rates and consequently protect against urinary leakage without higher risk of urinary retention. We expect this group to use less pads per day at the 6 week post-operative visit. We do anticipate a higher risk of bladder neck constriction (BNC) would be expected as well in the long term given the smaller diameter anastomosis.

Study Purpose and Objectives

The purpose of this clinical study is to assess the effect of catheter size on post-operative catheter pain, urinary continence, urinary flow rates, PVR, IPSS and QoL scores, as well as long term complications. The details of data collection are described in the "Data Collection Procedures" section below. Study objectives will be measured by:

Primary Outcome:

- Mean catheter related pain score on POD5-7

Secondary Outcomes:

- IPSS and QoL Scores at 6 and 12 weeks
- Opioid use after discharge until POD7
- Pads per Day at 6 and 12 weeks
- Urinary flow rate at 12 weeks
- PVR at 12 weeks
- Long-term complications at 12 weeks, 1 and 2 years

Risks and Benefits

As with any major surgery done under general anesthesia, there is a certain amount of risk, including heart attack, stroke and death. Preoperative assessment of a patient's overall health is part of the surgical workup at Virginia Mason Medical Center. Prostatectomies, including those done with a robotic-assisted surgery system, are also associated with the risks of impotence, incontinence, bleeding, infection, and bladder neck contracture.

Restoration of erectile function varies by patient and can be supported through the use of medications such as Viagra and Cialis and other types of treatment such as intraurethral suppositories or intracavernous injections.

Urinary continence depends on the internal, involuntary sphincter and the voluntary striated external sphincter. The internal sphincter is removed during RALP, as it is anatomically at the junction of the prostate and bladder. Practicing Kegel exercises returns function to the external sphincter after RALP and leakage can be decreased or eliminated over several weeks or months.

We would expect catheter size to impact urinary flow rates according to Poiseuille's law, and several studies have shown this to be the case⁸. We also anticipate that risks of anastomotic stenosis may be influenced by catheter size. We anticipate return to urinary continence and pain scores may be influenced by catheter size, which is the purpose of the study. Specifically, if randomized to the 16Fr group, we anticipate a possible increased risk of decreased urinary flow or bladder neck contracture in the future. If randomized to the 20Fr group, we hypothesize a possible risk of increased catheter related pain and time to regain post-operative continence.

Study design

This is a physician-sponsored, randomized, prospective study of patients identified to receive RALP. Patients will be eligible for this study if they:

- Are identified as candidates for RALP
- Are greater than 18 years of age

Patients will be excluded from the study if they:

- Have filled a prescription for opioid medications in the last 2 months. This will be reviewed by the medical record prescription history.
- Have a known latex allergy or are suspected to have developed an allergic response to the latex catheter during their clinical course.
- In whom pre-operatively, the catheter is anticipated to be left in place greater than 14 days based on clinical decision
- Have a significant deviation from the normal operative protocol such as significant bladder neck reconstruction or conversion to open (these patients will be considered a screen fail during the operation and will not be randomized to a certain catheter size)
- Have a history of pelvic radiation

In addition, patients who have a significant deviation from the normal post-operative course such as pulmonary embolism, myocardial infarction, stroke, or other major complications that are unrelated to study intervention but would impact outcome measures may be excluded from data analysis and further data collection per investigator's discretion.

Patient recruitment

Patients seen in pre-operative consultation by Virginia Mason Medical Center urologists will be assessed by the consulting surgeon for protocol eligibility at the time of consultation. The consent form will be reviewed with the patient in person, or by phone, at least 24 hours prior to surgery to allow time for consideration and questions. Patients may sign the consent anytime in the pre-operative setting before medication has been administered.

Early Termination

Patients may be discontinued from the study, per investigator's discretion, if any of the following conditions are met:

- Catheter remains in place greater than 14 days post operatively
- Lost to follow up (patient cannot be reached to schedule a follow up appointment after 3 attempts)
- Patient withdrawal of consent

Data Collection Procedures

Patient follow-up visits are routine and will occur at approximately 1, 6, and 12 weeks post operatively. Specific time point and methods of data collection are described below:

Post-surgical pain scores will be determined using a visual analog scale (VAS) with patients rating their mean post-operative pain on a scale from 1- No Pain to 10- Worst Possible Pain (Figure 1). Patients will be asked to indicate their pain specifically related to the catheter on this

scale. This information will be collected at POD7 just prior to catheter removal. This will be done in clinic if the appointment is that day or by telephone/mail/email/fax if the patient's appointment is not that day. A post-operative form including the VAS pain scale (Figure 1) and a pre-paid mailing envelop will be given to the patient in their study packet.

Opioid use will be collected at POD7 using the post operative pain form (Figure 1). Patients will be asked to count the number of pills left in their opioid prescription to determine number of tabs taken from discharge to POD7. If the patient is discharged after POD1, opioids taken as an inpatient on POD2 from the medical record will be included in opioid use. All opioid data will be converted a standardized morphine equivalency for comparison.

Pads per day: The patient will be asked to indicate the number of pads per days they are using. This data will be collected at 6 and 12 week follow up visits. This will be done in clinic if the appointment is that day or by telephone/mail/email/fax/REDCap (patients contact information, including email address, will be obtained from Cerner when available or by asking patient) if the patient's appointment is not that day. We recommend use of the Depend® Incontinence Guard for men (<https://www.depend.com/mens-solutions/products/10544>), or a comparable generic version.

International Prostate Symptom Score (IPSS) and Quality of Life Score: This validated questionnaire is an 8 question (7 symptom questions + 1 quality of life question) written screening tool used to screen for, rapidly diagnose, track the symptoms of, and suggest management of the symptoms of prostate disease. This is a clinician rated, validated scale. It will be administered and scores collected at the 6 and 12 week follow up visits. This will be done in clinic if the appointment is that day or by telephone/mail/email/fax/REDCap (patients contact information, including email address, will be obtained from Cerner when available or by asking patient) if the patient's appointment is not that day.

PVR: Post void residual volumes will be measured by having the patient void to their best effort (into a uroflowmeter described below) and then using a standard suprapubic bladder scanner to measure the remaining urine volume immediately after voiding. This will be measured at the 12 week follow up visit per investigator's discretion if clinically indicated.

Urinary flow rates will be measured by using a uroflowmeter. The patient voids into the device and is records the max flow rate, void time, and voided volume. This will be be measured at the 12 week follow up visit per investigator's discretion if clinically indicated.

Post Operative Complications will be recorded during the hospital stay or at clinic follow up visits and include any significant deviation from the normal post-operative course. Transient and permanent complications will be evaluated as part of this trial. At the long term follow up visits at 1 and 2 years, investigators capture long term complications such as bladder neck contracture.

Timing of Data Collection

Follow up visit #1 will occur 7 days +/- 7 following discharge, although as indicated above, pain scores and opioid use will be collected on POD7 regardless of clinic visit day. If the clinic appointment is not on POD7, we will collect this data by telephone or by mail. Timing of catheter

removal will be determined by the surgeon and is not affected by the study. Follow up visit #2 will occur 6 weeks +/- 4 weeks following discharge. Follow up visit #3 will occur 12 weeks +/- 5 weeks following discharge to account for patient availability. Patients will have annual follow-up thereafter and long term complications such as bladder neck contracture (BNC) will be recorded at 1 and 2 years post treatment (+/- 3 months). No other study data will be collected at these long term follow up visits. The specifics of how data will be collected and analyzed for each outcome are listed below.

Duration of Study participation

It is estimated that each patient who enrolls in the study and completes the routine follow-up visits will be participating for approximately two years.

Treatment Methodology and Statistical Considerations

Patients will be randomized by chance to either a 16 French or 20 French catheter in a 1:1 ratio. Subjects will be randomly assigned to either the standard of care or multi-modal group using Microsoft Excel ® randomization function.

A 2 year follow-up was chosen to allow for transient postoperative abnormalities to resolve so that the incidence of both transient and permanent complications can be evaluated.

Statistical evaluation of this study was completed by Axio during protocol development to ensure proper design and statistical power. We will use an ANOVA statistical variance model to test the hypothesis that the 20Fr group will have a higher mean pain score than the 16 French group. Secondary outcomes will also be measured with ANOVA analysis.

Sample Size and Accrual

We performed a pilot study of 25 patients to assess catheter related pain after transurethral resection of the prostate. Using this data, we calculated an average and standard deviation for catheter related pain of 3.2 and 2.45 respectively. In order to detect a difference in pain score of 0.6 between groups, at a power of 80% and alpha of 5%, we determined 44 patients should be included. Predicting a dropout rate of 20%, we plan to enroll approximately 55 patients to achieve 44 patients with full participation.

Data Monitoring

The Clinical Research Program will assess the risk of this trial and will devise and implement an internal monitoring and/or auditing plan for this trial. This plan will be revised as necessary during the life of the trial based upon a variety of factors, including but not limited to: protocol amendments, staff turnover, enrollment metrics, and compliance issues noted. An interim data analysis at 15 patients will be performed to assess pads per day, pain scores between groups, and assess for any difference in complications. If there is a significant difference in major post-operative complications, or patient safety concerns, the study will be terminated.

Data Analyses

Variables to be included in data analysis include aspects of the patient's history as outlined above. Additionally, operative details such as bladder neck reconstruction, change in technique from the stand running robotic vesico-urethral anastomosis or other significant alterations from the standard RALP approach will be included.

Outliers will be double-checked for accuracy. Subjects lost to follow-up will be included in short-term analysis only. Missing post-op data will be evaluated on a case-by-case basis with likely only long-term data being an issue. Missing operative data will be clarified with the operating surgeon. Any data that are not able to be collected with reasonable efforts will not be considered protocol deviations. Data analysis will specifically include risk ratios with 95% confidence intervals for those factors outlined above.

DATA COLLECTION

Records Keeping

Records and data will be kept using a password protected database. Paper source, including signed Informed Consent Form (ICF), will be stored in a secure location for the duration of the trial and securely archived for 10 years following study closure.

Secure Storage of Data

After data collection only de-identified data sets will be used for analysis and further study.

HUMAN SUBJECTS

Institutional Review Board (IRB) Review and Informed Consent

This protocol, the ICF and any subsequent modifications will be reviewed and approved by the IRB at Benaroya Research Institute at Virginia Mason. A signed ICF will be obtained from each subject.

Subject Confidentiality

All study data will be recorded in a password protected database. All computer entry and networking programs will be done using SID's only. Paper source will be stored in a secure location with access limited to study staff, Clinical Research Compliance Department staff, and outside regulatory bodies such as OHRP and FDA. Clinical information will not be released outside of the study team without written permission of the subject, except as necessary for monitoring by CRP Compliance, the FDA, and/or OHRP.

Study Modification/Discontinuation

The study may be modified or discontinued at any time by the Principal Investigator, IRB, OHRP, the FDA or other Government agencies as part of their duties to ensure that research subjects are protected.

PUBLICATION OF RESEARCH FINDINGS

Publication of the results of this trial will be governed by the policies and procedures developed by the Clinical Research Program. Any presentation, abstract, or manuscript will be made available for review by the Benaroya Research Institute prior to submission. No patient identifying information will be included in any publication or presentation of study results.

Figure 1 – Post-Operative Form

[figure not shown]
Virginia Mason Post-Operative Catheter Symptom Assessment

Name: _____

Date of Surgery: _____

Please fill out the following form on the 7th day after surgery (day of surgery is day 0, not 1)

1. Please circle your average catheter pain level at home within days 5-7 after surgery:

2. Please indicate how many tablets of opioids (oxycodone) you have taken at home (not in the hospital) in the first week since leaving the hospital. _____ tabs

Thank you for taking this survey. Please mail it back to Virginia Mason Urology using the pre-paid envelope included in your packet. If you lost the envelope, or you have questions, please call us at [contact].

REFERENCES

1. Centers for Disease Control (CDC). NATIONAL HOSPITAL DISCHARGE SURVEY. (2012).
2. Sammon, J. D. *et al.* Long-term follow-up of patients undergoing percutaneous suprapubic tube drainage after robot-assisted radical prostatectomy (RARP). *BJU Int.* **110**, 580–585 (2012).

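### The protocol describes no masking to catheter size, although the primary outcome is the patient's own rating of catheter pain and the 20 Fr catheter is expected to hurt more

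*Combined protocol and SAP*

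**What the plan says.** The protocol's Study Purpose and Objectives section names the primary outcome as "Mean catheter related pain score on POD5-7". Data Collection Procedures has "patients rating their mean post-operative pain on a scale from 1- No Pain to 10- Worst Possible Pain" and adds "Patients will be asked to indicate their pain specifically related to the catheter on this" scale. The Post-Operative Form (Figure 1) likewise asks the patient to circle his average catheter pain for days 5 to 7. The form may be completed in clinic or returned by mail, and the score may also be taken by telephone, email or fax.

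The expected direction appears in three places:
- The introduction says: "We hypothesize that patients with a smaller catheter will have improved pain scores and less opioid use".
- Risks and Benefits says: "If randomized to the 20Fr group, we hypothesize a possible risk of increased catheter related pain".
- Treatment Methodology and Statistical Considerations makes higher mean pain with 20 Fr the hypothesis to be tested.

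The design sentence reads: "This is a physician-sponsored, randomized, prospective study of patients identified to receive RALP". Neither it nor the sections on randomization, data collection and analysis mention masking of patient, staff, collector or analyst. No reason for leaving anyone unmasked is given.

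The timing of randomization is described in two ways. The exclusion list under Study design says that patients with a significant operative deviation are screen failures during surgery and are not randomized. The Schedule of RALP Study Procedures and Assessments marks randomization in the screening column (Day -28 to 0) and leaves it blank in the separate Day 0 column, where the operation is marked.

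**The concern.** The patient is asked how much of his discomfort comes from the randomized device. That judgement is open to suggestion if he knows which size he has and which size is thought to hurt more. A staff member who takes the score by telephone or in clinic and knows the arm could add to this.

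Any such effect would point the same way as the hypothesis, so it could not be separated from a true effect of size. Tablets of opioid taken at home are also self-reported, with less use predicted for the smaller catheter. Pads per day at 6 and 12 weeks are self-reported too, with fewer predicted for the smaller catheter. At stake is whether a difference in pain can be credited to catheter diameter.

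**Working it through.** **1. Is masking described?** Setting the sections side by side:
- Who rates: the patient (Data Collection Procedures; Figure 1).
- What is rated: pain attributed to the catheter.
- Expected direction: worse with 20 Fr (introduction; Risks and Benefits; Treatment Methodology and Statistical Considerations).
- Who knows the size: not stated anywhere.

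**2. Is masking possible?** Risks and Benefits places the operation among those it describes in the words "As with any major surgery done under general anesthesia". Both arms receive a urethral catheter and differ in size. If allocation follows the intra-operative screen, as the exclusion list implies, the patient is asleep when the size is chosen. If allocation happens at screening, as the schedule shows, the size could be known before surgery.

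**3. The plan's own figure.** From Sample Size and Accrual: target difference 0.6, SD 2.45, power 80%, alpha 5%, 44 patients.
- n per arm = 2 × (1.960 + 0.842)² × 2.45² / 0.6² = 2 × 7.849 × 6.0025 / 0.36 = 261.7, so 262 per arm (two-sided).
- The stated 44 does not reproduce. That is a separate problem, but it makes 0.6 a weak yardstick here.
- The dropout step does reproduce: 44 / 0.8 = 55.
- In SD units the target is 0.6 / 2.45 = 0.245.

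**4. What would an assumed bias do?** The documents give no size for an expectation effect, so b is an assumption, examined from 0 to 0.6 points. Suppose no true difference, 22 per arm (44 split 1:1) and a two-sided 5% t-test, which is what a two-group ANOVA amounts to.
- SE = 2.45 × √(2/22) = 0.739.
- Critical t on 42 degrees of freedom = 2.018, so the smallest observed difference reaching significance is 2.018 × 0.739 = 1.49 points.
- P(p<0.05) comes from the noncentral t distribution with noncentrality b / 0.739.

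| Assumed bias b (points) | b / SE | P(p<0.05) |
|---|---|---|
| 0 | 0 | 5.0% |
| 0.2 | 0.271 | 5.8% |
| 0.3 | 0.406 | 6.8% |
| 0.6 | 0.812 | 12.5% |

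**5. Would more patients help?** With 262 per arm, SE = 2.45 × √(2/262) = 0.214. A pure bias of 0.3 would then be significant in about 29% of trials, and one of 0.6 in about 80%. The bias in the estimate stays at b whatever the sample size; only the random error around it shrinks.

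**The case against.** The strongest reply is that silence is not an open-label design. Title and consent pages are not in the reviewed text, and nothing says whether patients are told their size or the expected direction. This stands: the supportable statement is that no masking is described.

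A reader might also infer that expectation alone could produce a difference as large as the 0.6 target, or that the trial is likely to give a false positive. The documents support neither. No figure for expectation bias is given, so choosing 0.6 as the upper end of a range is an assumption and cannot serve as evidence. Even a full 0.6-point bias would leave about 87.5% of trials at the planned size non-significant.

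Collector influence should not be overstated. A self-completed form with a prepaid envelope is in the patient's packet, and opioid use is meant to rest on a count of remaining pills. This limits the collector's part but does not remove the patient's, and the form itself simply asks how many tablets were taken.

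Finally, the feasibility argument leans on intra-operative randomization, which the schedule contradicts. That stands, and is why the timing must be settled as part of the correction.

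**Conclusion.** The point holds as a gap in the design. A subjective, device-attributed primary outcome with a declared expected direction has no described protection against knowledge of the arm. The main consequence is a primary estimate, and an opioid comparison, that may be biased toward the hypothesis by an unknown amount.

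The figures of 5% to 12.5% rest on an assumed bias of 0 to 0.6 points, no true effect, the transurethral-resection pilot SD of 2.45, 22 evaluable patients per arm and a two-sided test. The protocol does not state sidedness. The case for masking does not depend on those percentages. Enlarging the trial to repair its power would make a given bias more likely to reach significance. The gap should be closed, because the remedy is cheap and no analysis of the data as planned can recover what masking would have protected.

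**What to change.** 1. State in the protocol that patients are not told the catheter size until the POD7 form is returned, that the size printed on the catheter is covered at placement, and that whoever collects the POD7 score does not look up the arm. Keep the size in the chart and disclose it whenever care needs it.
2. Reconcile the exclusion list under Study design with the schedule on when randomization happens, so that allocation is not known to the patient before surgery.
3. For pads per day, extend non-disclosure to the week 6 and week 12 reports where feasible, or state that these outcomes are unmasked. Masking that ends at POD7 does not protect them.
4. Optionally, add a form item asking which size the patient believes he has, and report it descriptively as a check on masking. Do not stratify the primary result by it: a man in more pain may guess the larger size, so the guess can be a consequence of the outcome.
5. If masking is rejected, give the reason and show how the primary result changes over a range of assumed reporting bias.

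The cost is protocol and packet wording, a covering for the printed size and, if wanted, one form item. No added procedure is needed. The downside is that masking will be imperfect and may be broken for clinical care.

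### After catheter assignment, the investigator may drop patients with major complications from analysis and follow-up, which can remove events the trial compares

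*Combined protocol and SAP*

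**What the plan says.** All references are to the combined protocol and SAP.

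- **Study design, after the exclusion list.** Patients with a marked departure from the usual recovery are covered. Lung embolism, heart attack and stroke are given as examples, and the text continues: "or other major complications that are unrelated to study intervention but would impact outcome measures may be excluded from data analysis and further data collection". The decision is left to the investigator.
- **Data Collection Procedures, Post Operative Complications.** Recorded complications "include any significant deviation from the normal post-operative course". The same paragraph adds: "Transient and permanent complications will be evaluated as part of this trial".
- **Secondary Outcomes.** The list includes "Long-term complications at 12 weeks, 1 and 2 years".
- **Data Monitoring.** At 15 patients the arms are compared on pads, pain and complications. "If there is a significant difference in major post-operative complications, or patient safety concerns, the study will be terminated".
- **Data Analyses.** "Subjects lost to follow-up will be included in short-term analysis only". Risk ratios with 95% confidence intervals are planned.

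By contrast, patients with major deviations during the operation are treated as screen failures and are not randomised.

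**The concern.** Randomisation protects a comparison only while the randomised patients stay in it. This clause allows removal after assignment, for a reason defined partly by its effect on the outcomes, on a judgement about relatedness. Nothing in the documents says the person judging is masked to catheter size or to outcome.

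Three things are at stake:

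- **The complication comparison.** A patient removed from analysis takes the triggering event out of the count and themselves out of the denominator. If removals differ by arm or depend on outcome, the risk ratio is biased in either direction.
- **Later outcomes in the same patient.** Bladder neck contracture does not trigger removal, but it would go unrecorded at 12 weeks, 1 year and 2 years in a patient already removed. The protocol expects contracture to be more frequent with the smaller catheter.
- **The interim look.** Read plainly, exclusion from data analysis could also apply there. Data Monitoring does not say.

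**Working it through.** **Reading the passages together**

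1. *Timing.* The clause concerns post-operative events, so it acts after assignment. This is so whether randomisation is at screening, as the schedule shows, or during surgery, as the screen-failure wording implies.
2. *Conditions.* Removal is optional. It needs a major complication judged both unrelated to the catheter and likely to affect the outcomes.
3. *Overlap.* The trigger and the definition of a recorded complication use nearly the same words. The overlap is partial: the definition takes in any such deviation, while the clause adds the two conditions. Everything the clause can remove is nevertheless a complication the trial says it will evaluate.
4. *Limits elsewhere.* None was found. Patients lost to follow-up keep their short-term data; patients removed under this clause have no such protection.

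**Arithmetic (illustration only)**

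The plan states no complication rate, so event counts and who is removed are assumptions. From Sample Size and Accrual: 44 evaluable patients (22 per arm), about 55 enrolled (44/(1 − 0.20) = 55, which reproduces), pain mean 3.2, SD 2.45, target difference 0.6. Whether 44 is enough is a separate question, and the figure is used here only as the planned size.

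*Complications.* Assume 3 events per arm, and remove k event patients from one arm only. That arm's risk becomes (3 − k)/(n − k), divided by 3/n in the other arm.

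| n per arm | k | Affected arm | Other arm | Risk ratio |
|---|---|---|---|---|
| 22 | 0 | 3/22 = 13.6% | 13.6% | 1.00 |
| 22 | 1 | 2/21 = 9.5% | 13.6% | 0.70 |
| 22 | 2 | 1/20 = 5.0% | 13.6% | 0.37 |
| 27 | 1 | 2/26 = 7.7% | 11.1% | 0.69 |
| 27 | 2 | 1/25 = 4.0% | 11.1% | 0.36 |

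*Patients within reach.* At assumed major-complication rates of 2%, 5% or 10%, 55 × rate = 1.1, 2.8 or 5.5 patients over both arms, before the two conditions apply.

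*Interim look.* Assume arms of 7 and 8 and a two-sided Fisher test. Against no events in the other arm, 3/7 or 4/8 gives p = 0.077, so significance needs 4/7 or 5/8 (p = 0.026 each). Removing one event patient gives 3/6 v 0/8, p = 0.055, or 4/7 v 0/7, p = 0.070.

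*Pain, mean shift.* Remove k patients scoring one SD above the mean (3.2 + 2.45 = 5.65) from one arm of 22. The shift is −k × 2.45/(22 − k): −0.12, −0.25 and −0.39 for k = 1, 2, 3. The target is 0.6 and the standard error of the difference is 2.45 × √(2/22) = 0.74.

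*Pain, false-positive rate.* Simulation with no true difference, 22 per arm before removal, two-sided t-test at 5%, 200,000 runs:

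| Removed from one arm | k = 1 | k = 2 | k = 3 |
|---|---|---|---|
| Highest k, normal scores | 6.8% | 9.8% | 14.0% |
| Highest k, scores bounded 1–10 (scaled beta, same mean and SD) | 7.6% | 12.7% | 20.0% |
| k at random | about 5% | about 5% | about 5% |

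These are examples, not bounds.

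**The case against.** - **The clause is narrow.** It covers major events judged unrelated, its named examples are not urological, and contracture, the expected long-term harm, is not a trigger. This stands as a description. It does not remove the problem: relatedness is the judgement at issue, and a randomised comparison exists so that events need not be attributed case by case.
- **The event would normally be on record.** Complications are recorded in hospital and at visits, and the clause stops only further collection. This stands in part. The event may be in the file, but the patient may still be left out of the analysis, and later outcomes are not collected.
- **The illustrations are chosen.** A risk ratio of 0.37 needs two of three event patients removed from one arm and none from the other. The 7% to 20% error rates need the highest pain scores removed from one arm, and nothing in the clause selects on catheter pain. With removal at random from the upper half of one arm (normal scores), the rate is only about 5.0%, 5.5% and 6.1% for k = 1, 2, 3. This stands, and it is why the pain threat is put second.
- **The interim point is weak.** Only an extreme imbalance could reach significance at 15 patients, with or without the clause, and the patient-safety ground for termination needs no count. This stands.
- **Early Termination differs.** It speaks of discontinuing patients, not of excluding them from analysis. This stands, so the 14-day catheter rule is only a secondary point.

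**Conclusion.** The concern holds. As written, the clause lets an investigator remove randomised patients from the analysis and from follow-up because of complications, in a trial that compares complications, and no other section limits it. It should be fixed.

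The main threat is to the complication comparison and to the 12-week to 2-year data. With about 22 patients per arm, one or two one-sided removals are enough to turn an assumed risk ratio of 1.00 into 0.70 or 0.37. The effect on the primary pain comparison is probably smaller: close to nil if removal is unrelated to the score, larger only under strong selection. The actual bias cannot be computed. Its size and direction depend on event rates and on decisions that the documents do not give.

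**What to change.** Replace the clause under Study design with wording such as:

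> Patients with post-operative complications remain in data collection to 2 years unless they withdraw consent. The primary analysis compares arms as randomised, using every randomised patient with a POD5-7 pain score; missing scores are reported by arm with reasons. All complications count as outcomes whatever their attribution, including at the interim look. Any analysis that excludes patients with unrelated complications is a labelled sensitivity analysis, with exclusions decided masked to arm and outcome.

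The primary set is still limited to patients with a score. Reporting missing scores by arm shows any imbalance but does not correct it.

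As a secondary point, apply the same retention in data collection and analysis to two further groups. The exclusion list includes patients "suspected to have developed an allergic response to the latex catheter during their clinical course", which can arise only after a catheter is in place. Early Termination lists "Catheter remains in place greater than 14 days post operatively". This concerns data and analysis only; clinical care is unchanged.

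The cost is low: a wording change, continued follow-up of a few patients on visits the protocol already calls routine, and one extra sensitivity analysis. Some of these patients may be unable to complete the forms and would be reported as missing. Unrelated complications may add some noise to the pain score.
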